### **3.1 Safety Information**

In 2008, the FDA issued an early communication about an ongoing safety review of TNF blockers and the development of lymphoma and other cancers in children and adolescents.

As of the December 2009 FDA Pediatric advisory committee, it was noted that in general, adverse events seen in studies submitted for the JIA indication were similar to those in the adult population, both in type and frequency.

Due to the relatively rare occurrence of these cancers, the limited number of pediatric patients treated with TNF blockers, and the possible role of other immunosuppressive therapies used concomitantly with TNF blockers, the FDA was unable at that time to fully characterize the strength of the association between using TNF blockers and developing a malignancy. Product labeling for all anti-TNF agents now includes language regarding the risk of pediatric malignancies as requested by the FDA.

Furthermore, in November 2011 the FDA requested that all manufacturers of TNF inhibitors undertake a coordinated effort to better understand the risks for malignancies that develop in patients who are 30 years of age and younger at the time of diagnosis. Reporting requirements for these events can be found in Section 7.1.8 Serious Adverse Event Reporting. A detailed discussion of the clinical toxicology, metabolism, pharmacology, and safety experience with adalimumab can be found in the current SmPC.

### **4.0 Rationale**

Humira is approved in the US for reducing signs and symptoms of moderately to severely active polyarticular juvenile idiopathic arthritis in patients 2 years of age and older. Humira can be used alone or in combination with methotrexate (MTX).

In the EU, Humira in combination with methotrexate is indicated for the treatment of active polyarticular juvenile idiopathic arthritis, in patients 2 years of age and older who have had an inadequate response to one or more disease-modifying anti-rheumatic drugs

(DMARDs). Humira can be given as monotherapy in case of intolerance to methotrexate or when continued treatment with methotrexate is inappropriate.

This protocol describes a post-marketing observational registry that will evaluate the long-term safety and effectiveness of Humira as used in routine clinical practice in patients with moderately to severely active polyarticular or polyarticular-course JIA, who are candidates for anti-TNF therapy. This registry is part of a post marketing commitment from AbbVie to the Food and Drug Administration (FDA), and to the European Medicines Agency (EMA).

The participating physicians, with regard to countries and sites, will be representatives of the pediatric rheumatologists who will prescribe Humira to patients with moderately to severely active polyarticular or polyarticular-course JIA in the US, Europe, and Australia. The patients enrolled in this registry correspond to the target population as described in the current approved Humira label for polyarticular JIA in the participating countries.

The data collected in this registry will be complementary to those from the pre-registration study of Humira in moderately to severely active polyarticular or polyarticular-course JIA. The management of the patients in this registry will be reflective of Humira use for moderately to severely active polyarticular or polyarticular-course JIA post-approval in a routine clinical setting. The participating physician is free to determine the appropriate therapy for each patient. Only after this decision has been made, will the patient be offered participation in the registry.

Patients who consent to participate in the registry, will be followed for up to 10 years starting from Day 1 in the registry arm, providing long-term safety data for 10 years and long-term effectiveness data for 5 years. For the patients in the HUMIRA registry arm after having been initially in the MTX registry arm, the 10 year follow-up will restart from Day 1 in the HUMIRA registry arm.

## 5.0 Registry Objectives

The primary objective of this registry is to evaluate the long-term safety of Humira in patients with moderately to severely active polyarticular or polyarticular-course JIA who are prescribed and treated in accordance with the approved local Humira product label under the conditions of a routine clinical setting. Patients being prescribed and treated with MTX per the approved local product label will be considered a reference group.

The secondary objective of this registry is to evaluate the long-term effectiveness of Humira in patients with moderately to severely active polyarticular or polyarticular-course JIA who are prescribed and treated in accordance with the approved local Humira product label under the conditions of routine clinical setting. In addition, the impact of treatment interruptions on the safety and effectiveness of Humira will be evaluated as well. Patients being prescribed and treated with MTX per the local product label will be considered a reference group.

## 6.0 Investigational Plan

Patients, who agree to participate in the registry, will be followed for up to 10 years (within a registry arm), including patients who discontinue Humira (monotherapy or combination therapy with MTX) or MTX (without Humira). For patients who switch from the MTX arm to the Humira arm, the 10-year follow-up period will start at the time of enrollment into the Humira arm. This registry will assess the incidence and rate of Humira (monotherapy or combination therapy with MTX) or MTX observational and treatment-emergent SAEs, Adverse Events of Special Interest (AESI) and Pregnancy in patients diagnosed with moderately to severely active polyarticular or polyarticular-course JIA through Year 5. AESI are listed in Section 7.1.4 of this protocol. Starting at Year 6, patients will be followed annually for SAEs, a subset of AESI that includes congestive heart failure (CHF), malignancies, AEs at least possibly related to and/or leading to discontinuation of registry treatment, and pregnancies through Year 10. For polyarticular JIA patients 2 to < 4 years of age in countries with available local approval for this group

of patients at the time of consent to the registry, SAEs, all AESI, and pregnancy (at the age when a patient can become pregnant) will be collected for the full 10 years.

Patients who have discontinued or will discontinue from the registry (prior to completion of 10 years) will be contacted to determine interest in enrollment into the direct to HCP (Health Care Provider) follow-up process as described in Section 6.2. AESI, hospitalizations, surgeries and death as listed in Section 7.1.3 and Section 7.1.4 will be collected through Year 5 for those patients who choose to participate in the direct to HCP follow-up process. Starting at Year 6, patients will be followed annually for congestive heart failure, malignancies, hospitalizations, surgeries, and death through Year 10. Any other AEs, SAEs, and/or pregnancies should be reported according to normal spontaneous reporting procedures, and they are not subject to the requirements of this protocol. In countries with available local approval at the time of consent, polyarticular JIA patients 2 to < 4 years of age who discontinue for any reason, will be offered the opportunity to participate in the direct to HCP follow-up process and will be followed for AESI, hospitalizations, surgeries, and death annually for the full 10 years.

## **6.1 Selection of Population**

Once a decision has been made between the physician and the patient to use Humira (monotherapy or combination therapy with MTX) or MTX (without Humira) as part of usual care for and in accordance with approved local prescribing information for polyarticular JIA, sites will be encouraged to offer enrollment to all eligible patients. After a decision to prescribe Humira, patients from previous Humira clinical trials (Study M10-444 and Study DE038) will be offered enrollment in the registry. Prior to collecting registry-related information, a parent or legal guardian must sign a parental consent and patient assent/authorization form, or appropriate forms per local requirements for release of information. Physicians should determine the appropriate therapy for each patient without regard to study participation. The participating physician will provide the patient a prescription for Humira (monotherapy or combination therapy with MTX) or MTX (without Humira) along with instructions for appropriate use in patients with moderately to severely polyarticular JIA.

Patients prescribed Humira rolling over from another AbbVie clinical study will continue in the Humira arm.

New patients may be enrolled in one of two arms, the Humira arm or the MTX arm, depending on the treatment decision made by the physician prior to enrollment.

Patients in the Humira arm may be treated with Humira alone or in combination with MTX.

Patients in the MTX arm may be treated with MTX alone or in combination with other DMARDs, but not with anti-TNFs or other biologic therapies.

Patients who are non-responders, intolerant to MTX treatment arm or are in need of combination treatment with Humira therapy are eligible to switch to the Humira treatment arm up until enrollment of the last patient into the registry (i.e., until enrollment in the Humira treatment arm is complete).

In these cases patients will be required to discontinue from the MTX arm and consent as a new patient in the Humira arm once any Adverse Events of Special Interest and SAEs have been resolved or the AbbVie Study Designated Physician should be contacted to assess the eligibility of a patient to enroll in the Humira treatment arm if an AE is ongoing and eligibility criteria are met.

The 10-year follow-up time for these patients begins when these patients start the Humira arm and not the date they started the registry within the MTX arm.

After the registry enrollment period is closed to the Humira arm, patients wishing to switch to Humira will be discontinued from the MTX treatment arm; however, the patient will be encouraged to remain in the registry and efforts will be made to follow these patients through Year 10 to gather safety data.

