3. Patients who were treated in the MTX arm of this registry and prematurely discontinued from the MTX arm due to being a non-responder, or became intolerant of MTX treatment or are in need of combination treatment with Humira therapy may be eligible to enroll into the Humira treatment arm if all ongoing AEs/SAEs have been resolved, and they meet inclusion criteria and can enroll during the registry enrollment period. In case of ongoing AEs/SAEs at the time of the treatment arm switch, the AbbVie Study Designated Physician should be contacted to assess the eligibility of patient to roll into Humira treatment arm.
4. Parent or guardian has voluntarily signed and dated an informed consent/patient authorization form, approved by an Institutional Review Board (IRB)/Independent Ethics Committee (IEC) if applicable according to local law, after the nature of the registry has been explained and the patient's parent or legal guardian has had the opportunity to ask questions. Pediatric patients will be included in all discussions as per applicable local regulations in order to obtain verbal or written assent.

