### **7.1.2 Adverse Event Definition**

An adverse event (AE) is defined as any untoward medical occurrence in a patient, which does not necessarily have a causal relationship with their treatment. An AE can therefore be any unfavorable and unintended sign (including an abnormal laboratory finding), symptom, or disease temporally associated with the use of a medicinal product, whether or not the event is considered causally related to the use of the product.

Such an event can result from use of the drug as stipulated in the labeling, as well as from accidental or intentional overdose, drug abuse, or drug withdrawal. Any worsening of a pre-existing condition or illness is considered an AE. Laboratory abnormalities and changes in vital signs are considered to be AEs only if they result in permanent or temporary discontinuation of treatment with Humira or MTX, necessitate therapeutic medical intervention and/or if the Physician considers them to be AEs.

An elective surgery/procedure scheduled to occur during the registry will not be considered a SAE if the surgery/procedure is being performed for a pre existing condition and the surgery/procedure has been pre planned prior to entry to the registry. However, if the pre existing condition deteriorates unexpectedly during the registry (e.g., surgery performed earlier than planned), then the deterioration of the condition for which the elective surgery/procedure is being done will be considered an AE.

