### 7.1.3 Adverse Events of Special Interest

The Physician will monitor each patient for clinical and laboratory evidence for pre-defined Adverse Events of Special Interest at the Baseline visit and on a routine basis through Year 10 of the registry as mentioned in Section 6.5 Registry Duration.

AEs of Special Interest for this registry include:

Serious and nonserious opportunistic infections including the following bacterial, fungal, viral, and parasitic infections: Aspergillus, Blastomyces, Candida, Coccidioides, Cryptococcus, Cytomegalovirus, Histoplasma, Listeria, Nocardia, Paracoccidioides, Pneumocystis, Toxoplasma, Tuberculosis, Herpes, Bacillary angiomatosis, Mucormycosis, Progressive Vaccinia, Zygomycosis, BK virus, and JC virus.

Hypersensitivity reaction to Humira injection

Lymphoma

Hepatosplenic T-cell lymphoma

Non-melanoma skin cancer (NMSC)

Leukemia

Other malignancies (except lymphoma and NMSC)

Immune reactions including lupus, lupus-like reactions, and severe allergic reactions

CNS demyelinating disorders (including MS and Guillain-Barré syndrome and optic neuritis)

Hematologic events that are serious or lead to permanent discontinuation of treatment (e.g., aplastic anemia, granulocytopenia, granulocytes maturation Arrest, Leucopenia, Neutropenia, Pancytopenia, and Thrombocytopenia)

Hepatic events that are serious or lead to permanent discontinuation of treatment (e.g., persistent liver function test abnormalities, acute liver failure, and other serious hepatic events)

Vasculitis

Diverticulitis

Intestinal perforation

Congestive heart failure (CHF)

Severe CPK elevations (defined as CTC grade 3 and above) and associated clinical syndromes

New onset seizure disorders defined as any new epilepsy disorder diagnosed within the timeframe of the registry

Antiphospholipid syndrome and associated autoantibodies

New onset or worsening of Psoriasis

All events leading to premature discontinuation of treatment (Note: limited to only Adverse Events of Special Interest [listed above] leading to premature discontinuation for patients participating in the direct to HCP process)

All events that are probably or possibly related to treatment (Note: limited to only Adverse Events of Special Interest [listed above] that are probably or possibly related to treatment for patients participating in the direct to HCP process)

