### **10.3.1 Analysis of Observational SAEs and AEs of Special Interest**

The number and percent of patients experiencing SAEs and AEs of Special Interest during the registry, regardless of whether the AEs are reported during or after the Humira or MTX treatment, will be tabulated by body system and Medical Dictionary for Drug Regulatory Activities (MedDRA®) preferred term. Rates (event per 100 patient year of observation) of SAEs and AEs of Special Interest and the 95% confidence interval will be provided. The AEs summaries will also include SAEs and AEs of Special Interest collected through the HCP process. The last contact date is defined as the last date of registry or direct to HCP process participation, whichever occurs later.

The summaries will be provided using data from the first day in registry through the last contact irrespective of drug treatment duration.

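### Worsening of JIA that ends treatment counts as an AESI, so the AESI rates can mix lack of effectiveness with harm, and possibly more so in the MTX reference arm

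*Supplement*

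**What the plan says.** Three sets of rules in the protocol meet here.

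**What counts.** Section 7.1.2: "Any worsening of a pre-existing condition or illness is considered an AE". Section 7.1.3 then lists as an AESI: "All events leading to premature discontinuation of treatment". The only narrowing is for patients followed through the direct-to-HCP process, where this item is limited to the named AESI. For everyone else it is unrestricted. Section 6.0 keeps it in force after Year 5, when collection covers "AEs at least possibly related to and/or leading to discontinuation of registry treatment, and pregnancies through Year 10".

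**Who must leave an arm.** Section 6.1: "Patients in the Humira arm may be treated with Humira alone or in combination with MTX". For the other arm: "Patients in the MTX arm may be treated with MTX alone or in combination with other DMARDs, but not with anti-TNFs". An MTX patient who does not respond, is intolerant, or needs Humira added may switch while Humira enrollment is open, and then: "In these cases patients will be required to discontinue from the MTX arm and consent as a new patient in the Humira arm". Section 6.1.1, item 3, describes such patients as having "prematurely discontinued from the MTX arm due to being a non-responder". Once Humira enrollment closes, 6.1 still takes MTX patients who want Humira out of the MTX treatment arm, although they are encouraged to stay in the registry.

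**What is reported.** Section 10.3.1: "Rates (event per 100 patient year of observation) of SAEs and AEs of Special Interest and the 95% confidence interval will be provided". Sections 10.3.2 and 10.3.3 give the same kind of rate per 100 patient-years of exposure. Section 10.2 ends MTX exposure at the last MTX dose or the first Humira dose, whichever is earlier. Section 5.0 names the MTX patients as the reference group for the primary safety objective.

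**The concern.** An AESI rate should describe harm. Under these definitions it can also contain arthritis flares that ended treatment because the drug did not work well enough. That blurs the rate within each arm.

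It can also distort the comparison. A Humira patient with an inadequate response who is not already on MTX may have MTX added and remain in the arm, with no discontinuation to record. An MTX patient who needs Humira leaves the arm, and the exposure clock stops at the first Humira dose even if MTX continues. A site could reasonably record the flare behind that change as an event leading to discontinuation. If this happens more often on MTX than on Humira, the reference rate rises and Humira looks relatively safer. That is the less cautious direction for a registry that Section 4.0 describes as a post-marketing safety commitment.

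**Working it through.** **1. Does the text include JIA flares?** Sections 7.1.2 and 7.1.3 read together: worsening of an existing illness is an AE; an event that leads to early discontinuation of treatment is an AESI; JIA is not excluded in either place. So a recorded flare that ends MTX or Humira is an AESI. Section 6.8.1 lists lack of effectiveness as a reason for stopping, separately from AEs, but does not say that such a stop is not also recorded as an AE. Two sites could follow the protocol and record the same flare differently.

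**2. Does leaving the MTX arm trigger the rule?** The AESI item refers to discontinuing treatment; 6.1 refers to discontinuing from the arm. The documents point both ways:
- 10.2 ends MTX exposure at the first Humira dose, as if registry treatment had ended.
- 6.8.1 lists receipt of a biologic other than Humira as a reason for treatment discontinuation, and 6.6.4 treats Humira started after enrollment closes as a concomitant medication.

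The question is left open.

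**3. The plan's own figure.** The only sizing statement (10.6) gives about 97% power to detect 4.8 against 2.8 serious infectious AEs per 100 patient-years, with 1500 patient-years on Humira. Expected events are 0.028 × 1500 = 42 and 0.048 × 1500 = 72. An exact Poisson test rejects at 56 or more events and has 97.8% power, so the figure reproduces. It concerns serious infections against a fixed rate and says nothing about AESI or the MTX arm.

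**4. Illustration of size.** The documents give no AESI rate, no MTX failure rate and no recording rate. The inputs below are assumptions.
- Exit hazard: the 68% dropout in 10.6, read as constant over 5 years, gives −ln(0.32)/5 = 0.228 per year. For 500 Humira patients this yields 1492 patient-years, close to the stated 1500. Applying it to the 300 MTX patients is an assumption and yields about 895 patient-years.
- s = share of exits due to inefficacy; r = share of those recorded as a JIA-worsening AE.
- Added AESI per 100 patient-years = 100 × 0.228 × s × r.

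| s | r | Added per 100 patient-years | Events in 895 patient-years |
|---|---|---|---|
| any | 0 (reason code only) | 0 | 0 |
| 0.25 | 0.10 | 0.6 | about 5 |
| 0.50 | 0.25 | 2.8 | about 25 |
| 0.50 | 1.00 | 11.4 | about 102 |

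**5. Illustration of the contrast.** Assume equal true AESI rates of 5 per 100 patient-years, with s = 0.50 and r = 0.25. The MTX rate becomes 5 + 2.85 = 7.85. The Humira rate depends on how often its inefficacy cases exit:
- as often as on MTX: 7.85, ratio Humira/MTX 1.00
- 25% fewer, because MTX is added: 5 + 0.75 × 2.85 = 7.14, ratio 0.91
- 50% fewer: 5 + 0.50 × 2.85 = 6.42, ratio 0.82
- 25% more, for example through moves to another biologic: 5 + 1.25 × 2.85 = 8.56, ratio 1.09

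The last line shows that the sign is not fixed either.

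**The case against.** The strongest reply is that the protocol already keeps inefficacy apart from harm. Section 6.8.1 has a lack-of-effectiveness reason, 6.6.4 separates it from AEs for prior therapies, and non-response without worsening is not an AE under 7.1.2. If sites use the reason code alone, nothing is added. This stands as a limit on certainty, but it does not close the gap, because no section says the two recordings are alternatives.

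A reader might infer more than the documents support on three points.

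- **That the forced exit itself creates AESI.** It does not. Section 6.1 requires leaving the arm, and a child who adds Humira may continue MTX.
- **That the rule falls mainly on MTX.** The AESI definition is the same in both arms, and Humira patients who stop for a flare or change biologic count too. MTX patients can add other DMARDs and stay. Adding MTX is no way out for Humira patients who already take it or cannot tolerate it, and Section 4.0 gives the EU indication as combination use with monotherapy as the exception. Only the net difference between arms biases the contrast.
- **That the switch rule is circular**, because the flare behind the switch is an unresolved AESI. Sections 6.1 and 6.1.1 both provide for contact with the Study Designated Physician when an event is ongoing.

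It is also fair to say that the plan is descriptive, with no formal between-arm test, and that tabulation by preferred term would let a careful reader see JIA worsening. The separate SAP mentioned in 10.4.1.4 was not available and may group AESI further. The AE and AESI definitions, however, are set in the protocol and govern what sites record.

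**Conclusion.** The definitional gap is real: as written, JIA worsening that ends MTX or Humira is an AESI and enters the rates in 10.3.1 to 10.3.3. Given the one-sided add-on rule and the exposure cut at the first Humira dose, it is plausible that this raises the MTX reference rate more than the Humira rate. That is a risk, not a demonstrated bias. The documents yield no point estimate. The illustrated range of 0 to 11.4 added AESI per 100 patient-years on MTX, and the Humira/MTX ratios of 0.82 to 1.09, rest wholly on assumed failure, recording and exit rates and on borrowing the Humira dropout figure for MTX.

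The effect is confined to total AESI and to the category of events leading to discontinuation. Malignancy, congestive heart failure, opportunistic infection and serious infection (the sizing endpoint) are not affected. It deserves correction because the MTX arm is the reference for the primary safety objective and the remedy is cheap.

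**What to change.** 1. In 7.1.3 and 10.3, state that worsening of JIA or lack of effectiveness is recorded as the reason for discontinuation and is not counted under the AESI item for events leading to discontinuation, unless it meets SAE criteria.
2. State whether leaving the MTX arm to add Humira counts as discontinuation of treatment, so that 6.1, 6.6.4, 6.8.1, 7.1.3 and 10.2 agree.
3. Report AESI rates by arm with and without JIA-worsening preferred terms, and show those events on their own line.
4. Reconcile the switch provisions in 6.1 and 6.1.1, item 3, with the definitions in 7.1.2 and 7.1.3. Section 6.1 speaks of resolved AESI and SAEs, while 6.1.1 speaks of resolved AEs and SAEs. The request is only that these sections agree; it takes no view on what the switch rule should be.

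The cost is some wording and one extra table row per arm. Preferred terms and discontinuation reasons are already collected, so no new data are needed. The headline AESI rate will change, and showing it both ways keeps it comparable with any interim report already issued.
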